5. STUDY POPULATION

5.1. General

Patients enrolled in the study will be male and female patients, ≥ 18 to 75 years old, inclusive, with FM and an average of the daily average PI-NRS score of ≥ 4 and ≤ 9 during the last 14 days of the 14-day baseline assessment period.

For continuous variables, descriptive statistics (number [n], mean, SD, SE, median, minimum, and maximum) will be provided. For categorical variables, patient counts and percentages will be provided. Categories for missing data will be presented, if necessary.

The ITT analysis set will be used for all study population summaries unless otherwise specified. Summaries will be presented by treatment group and for all patients.

5.2. Patient Disposition

Descriptive statistics will be used to summarize data from the following groups: patients screened; patients screened but not randomized and reason not randomized; patients who are randomized; patients randomized but not treated (and reason); patients in the ITT, mITT, safety, and PP analysis sets; patients who complete the treatment and the study; and patients who discontinue from the treatment and the study. Data from patients who discontinue from treatment and the study will also be summarized by reason for discontinuation using descriptive statistics.

5.3. Demographics and Baseline Characteristics

Patient demographic characteristics (age, sex, ethnicity, and race) and baseline characteristics will be examined to assess the comparability of the treatment groups and will be summarized using descriptive statistics. No inferential analyses will be performed. Demographic and baseline characteristics will be summarized using ITT analysis set.

Baseline characteristics include

- age at time of FM onset or diagnosis of FM
- month since FM onset
- month since FM diagnosis
- alcohol history
- psychiatric history
- ECG findings at screening

Month will be calculated as (date of informed consent - the date of the event + 1)/30.42. Rules for handling partial dates are in Section 4.3.

5.4. Medical History

All medical history will be coded using the Medical Dictionary for Regulatory Activities (MedDRA). The incidence of medical history abnormalities will be summarized using descriptive statistics by system organ class (SOC) and preferred term. Patients are counted only

once in each preferred term and SOC category. Summaries will be presented by treatment group and for all patients.

5.5. Prior Therapy and Medication

Any prior therapy or medication will be coded using the World Health Organization (WHO) Drug Dictionary. The incidence of prior therapies and medications, past fibromyalgia medication will be summarized using descriptive statistics by therapeutic class and preferred term. Patients are counted only once in each therapeutic class category, and only once in each preferred term category. Prior therapies and medications will include all medications taken and therapies administered before the first day of study drug administration.

Past fibromyalgia medication will also be summarized separately.

5.6. Childbearing Potential and Methods of Contraception

For female patients, information related to childbearing potential and menopause will be collected at the screening visit. Data will be listed.

For female and male patients, methods of contraception will be collected at the screening visit. Data will be listed.

5.7. Study Protocol Deviations

All protocol deviations (PD) will be collected and entered in an excel spreadsheet. All PDs will be reviewed and approved by the study team prior to database lock. In addition, the important PDs will be also determined by study team before database lock. The important PDs will be summarized for overall and for each category using descriptive statistics and all PDs will be listed in a data listing.

6. EFFICACY ANALYSIS

6.1. General

The mITT analysis set will be the main analysis set for all efficacy analyses. The PP analysis set will serve as supportive analysis set for analyses of the primary efficacy endpoint and following selected secondary efficacy endpoints:

- responder rate of PGIC rating (percentage of patients much improved or very much improved) at week 12
- change from baseline to week 12 in the weekly average of the daily worst PI-NRS score over the past 24 hours
- the percentage of patients who experience a $\geq 30\%$ reduction in the weekly average of the daily average PI-NRS score at week 12
- the percentage of patients who experience a $\geq 50\%$ reduction in the weekly average of the daily average PI-NRS score at week 12

For efficacy summaries and analyses using the last visit, this last visit should not include the follow-up visit which was scheduled in Study TV48125-PN-20028 prior to protocol amendment 04. In addition, data collected after week 12 will be included in descriptive summaries but will not be included in any inferential analyses.

6.1.1. Pain Intensity-Numerical Rating Scale and Rescue Medication Use

The PI-NRS is an 11-point pain intensity numerical rating scale where 0=no pain and 10=worst possible pain. The PI-NRS will be used to rate average FM pain intensity over the past week at screening via the site tablet at the screening visit. From Visit 2 to Visit 7 the PI-NRS will be recorded in the patient's e-diary every evening (Evening Report) between 1800 and 2200 hours for the following:

- The average FM pain intensity over the past 24 hours
- The worst FM pain intensity over the past 24 hours

If a patient cannot complete or forgets to complete the Evening Report, a Make-up Evening Report will become available for completion between 0300h and 1300h the next day. In case both the Evening Report and the Make-up Evening Report are completed, PI-NRS collected on the Evening Report will be used for analyses.

The Rescue Medication tab on the e-dairy will be available to patients 24 hours per day. Patients will record the following in the e-diary:

- Time of rescue medication used for a specific breakthrough pain episode
- Amount (tablets) of rescue medication used for a specific breakthrough pain episode
- At-the-moment pain intensity just prior to the use of rescue medication

If a patient cannot record or forgets to record the rescue medication taken, the Evening Report will be used to record any missed rescue medication taken. A patient can take 1 to 2 caplets with dose up to 1000 mg, a maximum of 6 caplets(3000 mg) in a 24-hour period.

6.1.2. Baseline and Analysis Weeks for Data Collected Daily

Baseline is defined as the last 14 days before the first dose of IMP (day -14 to day -1). Day 1 will be defined as the day of first dose of IMP (Visit 3).

For data collected daily (eg. PI-NRS scores), analysis weeks will be derived using algorithm in Table 2. Analyses will be based on the derived analysis weeks.

Table 2: Analysis Weeks

4-Week Interval	Visit	Dose (n)	Target Injection or Visit Day	Actual Injection or Visit Day	Analysis Week	Analysis Week Interval
1 ^a	3	1	1	1	1	[1, v-22]
					2	[v-21, v-15]
					3	[v-14, v-8]
					4	[v-7, v-1]
2 ^a	4	2	29	v (2 nd dosing day)	5	[v, x-22]
					6	[x-21, x-15]
					7	[x-14, x-8]
					8	[x-7, x-1]
3 ^a	5	3	57	x (3 rd dosing day)	9	[x, y-22]
					10	[y-21, y-15]
					11	[y-14, y-8]
					12	[y-7, y-1]
4 ^b (last dose)	6	4	85	y (4 th dosing day)	13	[y, y+6]
					14	[y+7, y+13]
					15	[y+14, y+20]
					16	[y+21, y+27]
5	5	EOT	113		-	-

^a In 4-week intervals before the last dose, the 4th week will be 7 days before the date of the injection, and counting backward by 7-day increments to define remaining weeks. The 1st week of these 4-week intervals will include all remaining days in the interval.

^b The weeks after the last dose, an analysis week will be defined as a 7-day interval counting onward.

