6.1.3. Data Derivation for weekly average of PI-NRS

The weekly average of an efficacy variable in an analysis week will be calculated as follow:

$$\frac{\sum \text{non-missing efficacy variable in an analysis week}}{\text{Number of days with non-missing efficacy variable in the analysis week}} \quad [1]$$

Where the efficacy variable will be

- Daily average PI-NRS pain score over the past 24 hours
- Daily worst PI-NRS pain scores over the past 24 hours

If all of the data are missing within an analysis week, the average of the efficacy variable within the analysis week will be missing.

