6.2.2. Primary Efficacy Analysis

The primary efficacy endpoint will be analyzed using a MMRM model with change from baseline in the average of the daily average PI-NRS score over the past 24 hours at weeks 1, 2, 3, 4, 5, 6, 7, 8, 9, 10, 11, and 12 as the dependent variable, sex, age group at FM onset, week, treatment, and treatment by week interaction as fixed factors, and baseline average of the daily average PI-NRS score as a covariate. The heterogeneous autoregressive correlation structure [ARH (1)] for repeated observations within patients will be used, and the denominator degrees of freedom will be estimated using Kenward-Roger’s approximation. An adjustment for missing data due to lack of efficacy or adverse events assumes the PI-NRS scores will be on average return to baseline values. Missing data (due to early treatment discontinuation or missing e-dairy recording in an entire analysis week) will be imputed 500 times to generate 500 complete data sets using the SAS procedure PROC MI following the 3 steps below.

Notes, if ARH(1) does not converge, then simpler covariance structures with less parameters will be used in the following order until the model converges: autoregressive (1) (AR[1]); heterogeneous compound symmetry (CSH); and compound symmetry (CS).

Step 1: The monotone missing pattern will be induced by the Markov Chain Monte Carlo method in the PROC MI procedure using seed number 4751523.

The average of the daily average PI-NRS score up to and including week 12 will be imputed by using following SAS code to impute the arbitrary missing data and to make the missing data pattern monotonic:

```
PROC MI DATA=name NIMPUTE= 500 SEED=4751523 OUT= MI_MONOTONE;  
  BY TRT01PN AGEATFMONST SEX;  
  MCMC IMPUTE= MONOTONE;  
  VAR BASE WEEK1 ... WEEK12;  
RUN;
```

Where TRT01PN denotes the planned treatment group; AGEATFMONST denotes the age group at FM onset; BASE denotes the baseline average of the daily average PI-NRS score; WEEK1, . . . , WEEK12 denote the weekly average of the daily average PI-NRS score in weeks. In bold are the SAS key words.

Statistical Analysis Plan

Step 2: Once the arbitrary missing data are imputed, the following SAS code will be used to impute the monotone missing data.

The remaining missing data at subsequent weeks will be imputed using the regression method for the monotone pattern with seed number 4751523 and adjustment for covariates including baseline value and all values at preceding weeks.

```

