PROC MI DATA= MI_MONOTONE NIMPUTE= 1 SEED= 4751523
OUT= MI_COMPLETE;
  CLASS TRT01PN AGEATFMONSET SEX;
  MONOTONE REG;
  VAR TRT01PN AGEATFMONSET SEX BASE WEEK1 ... WEEK12;
RUN;
```

MI_COMPLETE will be transposed to a new data set (WEEKPI0) with each week as a row.

Step 3: Use by-week mean change from baseline to adjust those who discontinued treatment due to lack of efficacy (LOE) or adverse event (AE) before week 12.

The initially missing and now imputed data for patients who discontinued from the study drug due to LOE or AE will be center adjusted at the mean baseline value. That is, the final imputed score will be equal to the imputed score under missing at random minus the observed mean change from baseline score at the post baseline time point.

```
DATA WEEKPI;
  SET WEEKPI0;
  CHANGEi = AVALi - BASE;
  IF DTREAS IN ('LACK OF EFFICACY', 'ADVERSE EVENT') AND IMP= 1
  THEN DO;
    CHANGEi = CHANGEi - MWEEK_CHG;
  END;
RUN;
```

Where AVALi denotes the value of the post baseline weekly average of the daily average PI-NRS after missing data imputation; CHANGEi denotes the change from baseline after missing data imputation; MWEEK_CHG denotes the change from baseline calculated without missing data imputation; DTREAS denotes the reason for treatment discontinuation.

Step 4: Each of the 500 imputed data sets described above steps will be analyzed using the MMRM. SAS code is:

```
ODS OUTPUT LSMEANS= LS DIFFS = DIFF (WHERE = (week = _week));
PROC MIXED DATA= WEEKPI (WHERE= (WEEK>= 1));
  BY _IMPUTATION_;
  CLASS SUBJID TRT01PN WEEK AGEATFMONSET SEX;
  MODEL CHANGEi= BASE TRT01PN AGEATFMONSET SEX WEEK
    TRT01PN*WEEK/DDFM=KR;
  REPEATED WEEK/SUBJECT= SUBJID TYPE= ARH(1);
  LSMEANS TRT01PN*WEEK / DIFF CL;
RUN;
ODS OUTPUT CLOSE;
```

Statistical Analysis Plan

Where `_IMPUTATION_` denotes the numbering of imputations; `SUBJID` denotes the subject ID; `WEEK` denotes the analysis week (12 levels: weeks 1 to 12).

Step 5: The results from the 500 analyses from Step 4 will be combined using Rubin’s formulae (`PROC MIANALYZE`). The least square (LS) mean estimates for the mean change from baseline to each time point, as well as the difference of the estimates between the fremanezumab and placebo group, with the corresponding SE, p-value and associated 95% CI will be provided.

(a) For LS means

```
PROC SORT DATA= LS;  
  BY WEEK TRT01PN _IMPUTATION_ ;  
RUN;  
  
ODS OUTPUT PARAMETERESTIMATES= LSM_O;  
PROC MIANALYZE DATA= LS;  
  BY WEEK TRT01PN;  

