Where AVALCAT denotes the responses with ‘yes’ for $\geq 30\%$ or $\geq 50\%$ or ‘no’ for $< 30\%$ or $< 50\%$ pain intensity reduction, respectively.

The 500 sets of results from above analyses will be combined using Rubin’s formulae (PROC MIANALYZE).

```
PROC SORT DATA= LS;
```

Statistical Analysis Plan

```

    BY WEEK TRT01PN _IMPUTATION_ ;
RUN;

ODS OUTPUT PARAMETERESTIMATES= LSM_O;
PROC MIANALYZE DATA= LS;
    BY WEEK TRT01PN;
    MODELEFFECTS ESTIMATE;
    STDERR STDERR;
RUN;

DATA LSM_O;
    SET LSM_O;
    EXPESTIMATE = EXP(ESTIMATE);
    P = 100*EXPESTIMATE/(1 + EXPESTIMATE);
    P_LL = 100*EXP(LCLMEAN)/(1 + EXP(LCLMEAN));
    P_UL = 100*EXP(UCLMEAN)/(1 + EXP(UCLMEAN));
RUN;

```

In addition, the mean percentage of reduction and its associated 95% CI will be reported by week.

A plot of percentage of improvement versus percentage of patients meeting the improvement level at week 12 will be presented based on observed data and missing data at week 12 will be deemed as pain intensity increased from baseline. The x-axis representing percentage of improvement will be from ≥ 0 to 100% by an increment of 10%, ie., the x-axis will be at cutoff points $\geq 0\%$, $\geq 10\%$, $\geq 20\%$, ..., $\geq 90\%$ and 100% while y-axis will be percent of patients meet the cutoff points. The percentage of improvement will be calculated using formula [2].

6.3.4. Change From Baseline to Week 12 in the Weekly Average of the Daily Worst PI-NRS Score Over the Past 24 Hours

The weekly average of the daily worst PI-NRS score over the past 24 hours will be analyzed in a manner analogous to the primary endpoint as described in Section 6.2.2. The dependent variable is the change from baseline in the weekly average of the daily worst PI-NRS scores. The covariate will be baseline average of the daily worst PI-NRS scores.

6.3.5. Change From Baseline to Week 12 in the Patient-Reported Outcomes Measurement Information System Sleep Disturbance Short Form 8a Score

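### SAP Table 2 counts diary days twice (weeks 4/6 or 8/10) when doses are 20 days or less apart, and leaves week 1, 5 or 9 without days at 21 or less; week 12 is not affected directly

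*SAP*

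**What the plan says.** SAP Table 1 (section 4.4) places doses 1 to 4 on days 1, 29, 57 and 85, with ±7 days for doses 2, 3 and 4, each window fixed relative to day 1. Neither document states a minimum interval between doses. Protocol 5.1.1.2 lets the Medical Monitor lengthen a window.

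SAP Table 2 (section 6.1.2) assigns each diary day to an analysis week, with v, x and y the actual days of doses 2, 3 and 4. Footnote a gives the rule: "the 4th week will be 7 days before the date of the injection, and counting backward by 7-day increments to define remaining weeks". Then: "The 1st week of these 4-week intervals will include all remaining days in the interval". The printed limits are:

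- weeks 1 to 4: [1, v-22], [v-21, v-15], [v-14, v-8], [v-7, v-1]
- weeks 5 to 8: [v, x-22], [x-21, x-15], [x-14, x-8], [x-7, x-1]
- weeks 9 to 12: [x, y-22], [y-21, y-15], [y-14, y-8], [y-7, y-1]

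Section 6.1.3 covers a week without scores: "If all of the data are missing within an analysis week", the weekly average is missing. Section 6.2.2 describes missing data as arising from early discontinuation or from "missing e-dairy recording in an entire analysis week". Its imputation code runs over every week ("VAR TRT01PN AGEATFMONSET SEX BASE WEEK1 ... WEEK12"). The Step 3 code then shifts imputed values under the condition "IF DTREAS IN ('LACK OF EFFICACY', 'ADVERSE EVENT') AND IMP= 1". No rule covers a diary day that falls in two analysis weeks.

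**The concern.** In each of the three dosing intervals, three weeks have a fixed length of 7 days and are counted back from the next dose. They need 21 days, and the first week needs at least one more. If a late visit is followed by an early one, both inside their windows, fewer than 22 days may be available. Weeks 6 and 10 then reach back past the dose that opens their interval, into days already used for weeks 4 and 8, and the first week of the interval has no days at all.

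Two things follow. Some diary scores count twice. And a patient with a complete diary can have a week labelled missing, filled by imputation and, if that patient later stopped for lack of efficacy or an adverse event, moved toward baseline by Step 3, although the patient was on treatment and reporting pain at the time.

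The outputs at stake are those by week: the least-squares "mean estimates for the mean change from baseline to each time point" and the treatment differences in section 6.2.2, the responder results in section 6.3.3 ("the mean percentage of reduction and its associated 95% CI will be reported by week"), and the weekly descriptive summaries.

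**Working it through.** **1. The table at its target days.** With v=29, x=57, y=85, all 16 weeks have exactly 7 days and none overlap. The table does what it intends on schedule.

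**2. Gaps inside the ±7-day windows.** v runs from 22 to 36, x from 50 to 64, y from 78 to 92.
- Dose 1 to 2: 22-1=21 to 36-1=35 days.
- Dose 2 to 3: 50-36=14 to 64-22=42 days. Dose 3 to 4: 78-64=14 to 92-50=42 days.

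**3. Effect of the gap.** Week 1 has v-22 days, so it is empty only at v=22. Weeks 5 and 9 have gap-21 days, or none if that is not positive. Weeks 6 and 10 start 21 days before the next dose, so they overlap the preceding interval's last week by 21-gap days. Bounded by their own interval, they keep gap-14 days, at most 7.

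| Gap (days) | 22 | 21 | 20 | 15 | 14 |
|---|---|---|---|---|---|
| Days in week 5 or 9 | 1 | 0 | 0 | 0 | 0 |
| Days shared (weeks 4/6 or 8/10), as printed | 0 | 0 | 1 | 6 | 7 |
| Days in week 6 or 10, if bounded | 7 | 7 | 6 | 1 | 0 |

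Examples: with v=36 and x=56, week 4 is [29, 35], week 5 is [36, 34] (empty) and week 6 is [35, 41], so day 35 counts twice. With x=64 and y=78, weeks 8 and 10 are both [57, 63], and week 9 is [64, 56].

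**4. All in-window schedules**, 15×15×15=3,375.
- Empty week 1: v=22, 15×15=225.
- Empty week 5: gaps 14 to 21 arise from 1+2+...+8=36 pairs (v, x), times 15 values of y: 540. Week 9 likewise: 540.
- At least one empty week: 225+540+540, minus 36 schedules with weeks 1 and 9 both empty, minus 1 with weeks 5 and 9 both empty: 1,268.
- Shared days as printed: gaps 14 to 20 arise from 1+2+...+7=28 pairs, times 15: 420 for weeks 4/6 and 420 for weeks 8/10, never both: 840.
- Days left out of every week: 0. Schedules in which week 12 is short or shared: 0.
- With weeks bounded by their interval: 1,268 with an empty week, 0 shared; week 6 or 10 is also empty in 15+15=30.

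**5. The earlier ±3-day windows** (Protocol 16.3 dates the change to Amendment 04). v runs from 26 to 32, x from 54 to 60, y from 82 to 88. The shortest gaps are 25, 54-32=22 and 82-60=22. All 7×7×7=343 schedules have no empty week and no shared day.

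**6. Frequency in patients.** The documents do not give it. Assuming visit deviations truncated at ±7 days with SD 1/2/3/4 days, for every patient:
- independent: 0/2/12/21% have an empty week and 0/1/6/12% a shared day;
- correlation 0.5: 0/0.2/3.5/10% and 0/0/1/4%.

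**7. Effect on the treatment difference.** A simulation compared Table 2 as printed with weeks bounded by their interval and empty weeks left out. Assumptions: 3 arms of 80, effect -0.75 at day 84, 25% dropout with half of it for lack of efficacy or adverse event, and ±7 days for all. It approximates the SAP model (5 imputations instead of 500, no Kenward-Roger), with 60 runs per scenario.
- Week 12: mean change 0.000; largest 0.006 (independent deviations, SD 3) or 0.017 (uniform over ±7), against a sampling SD of 0.3.
- Weeks 1, 5, 6, 9 and 10: SD of the change 0.01 to 0.02 (SD 3) or 0.02 to 0.04 (uniform); largest 0.11.

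**The case against.** The strongest reply is that little depends on this. The primary and all timed secondary efficacy endpoints are at week 12, which is [y-7, y-1] and never touched. The study has already been stopped for futility (SAP 2.5.1), and there is no multiplicity-controlled claim. All of that stands.

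The ±7-day window also did not govern the whole trial. The amendment history records 68 patients at Amendment 04 and 153 at Amendment 05. Appendix O failed those in screening on 26 March 2020. If nobody was randomized between then and Amendment 04, the 68 (68/153=44%) had day 85 due by about 18 June 2020, almost entirely under ±3 days. For them a short gap needed a visit outside the window then in force. This stands too: the percentages in step 6 are upper-end.

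Footnote a can be read as already bounding weeks by their interval. That reading is reasonable and removes the sharing, but the printed limits [x-21, x-15] and [y-21, y-15] contain no bound, and the empty weeks remain under either reading. A reader might infer that two programmers would build different data for all of weeks 1 to 10. The documents do not support that: the two readings differ only in weeks 6 and 10.

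An empty week is not unhandled. Section 6.1.3 sets it to missing, and the printed code imputes it. Imputing it or leaving it out is a choice between workable methods. Step 3 also needs a distinction. Its text covers only patients who stopped before week 12. Week 9 can be empty only if dose 4 was given, and week 12 ends the day before dose 4, so by the text no shift applies to an empty week 9. Only the printed IF statement, which lacks that condition, would shift it. For an empty week 1 or 5 in a patient who stopped later but before week 12, text and code both apply the shift.

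**Conclusion.** Table 2 is wrong as printed for gaps that the visit windows allow: it counts diary days twice at 20 days or less, and it leaves week 1, 5 or 9 without days at 21 or less. This follows from the printed limits and needs no assumption. The severity is minor.

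Three stronger readings are tempting, and the documents do not support them. The primary result is not in doubt: weeks 1 to 11 reach the week-12 estimate only through the imputation model and the repeated-measures covariance, and the simulated change is negligible. The ratio 1,268/3,375=38% is a count of possible schedules, not a share of patients; the number of patients affected is unknown. No diary entry is lost: every day from 1 to y-1 falls in some week.

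The sizes given for patients and for weekly estimates rest on assumed visit deviations and on ±7 days for everyone, so they should be read as upper-end.

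**What to change.** Before database lock (SAP 2.5.2 allows amendments until then):

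1. Add to footnote a of Table 2 that no analysis week starts before its interval's own dosing day. Within the windows this changes only two lines: week 6 = [max(v, x-21), x-15] and week 10 = [max(x, y-21), y-15]. Each diary day then counts once. Stated as a general rule, it also serves a window lengthened by the Medical Monitor.
2. State in section 6.2.2 that a week left with no days by the algorithm is not a discontinuation-related missing value and gets no Step 3 shift.
3. Restrict the Step 3 IF statement to patients who stopped before week 12, so that the code matches its text.

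Whether the empty week is then imputed as missing at random or left out of the model is optional, but should be stated.

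The cost is a footnote, a sentence and a line of code. No visit or dosing window changes, and week 12 is the same in all 3,375 schedules. The downside is that week 6 or 10 rests on 1 to 6 days at gaps of 15 to 20 and is empty at gap 14.
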